5.1 Inclusion and Exclusion criteria

Patients must have baseline evaluations performed prior to the first dose of study drug and must meet all inclusion and exclusion criteria. Results of all baseline evaluations, assuring that all inclusion and exclusion criteria have been satisfied, must be reviewed by the Principal Investigator or his/her designee

prior to enrollment of that patient. In addition, the patient must be thoroughly informed about all aspects of the study, including the study visit schedule and required evaluations and all regulatory requirements for informed consent. The written informed consent must be obtained from the patient prior to enrollment. The following criteria apply to all patients enrolled onto the study unless otherwise specified.

1. Participants must have ≥ 18 years of age.
2. Participants must have an elevated risk of breast cancer as defined by at least one of the following categories and have declined tamoxifen, raloxifene and/or aromatase inhibitor therapy:
 - a. Diagnosis of LCIS, atypical ductal or lobular hyperplasia.
 - b. A known deleterious mutation in *BRCA1*, *BRCA2*, *PTEN* or *TP53*. (Note: The participant must be a documented carrier to meet this criterion. If there is a known mutation in a hereditary breast cancer susceptibility gene in a participant's family member, the participant herself must have undergone genetic testing as per NCCN clinical guidelines to be eligible per this criterion.) Known mutation in *PALB2* or *CHEK2* del 100C or any germline mutation.
 - c. Modified Gail/CARE model risk at 5 years $\geq 1.67\%$. (Note: Risk models are to be used only if there is no known previous diagnosis of resected DCIS or LCIS and there is no known deleterious mutation in *BRCA1*, *BRCA2*, *PTEN* or *TP53*).
 - d. 10% or more probability of BRCA mutation by BRCAPRO or similar model
3. Participants must have at least one breast available for imaging and biopsy. A previously irradiated breast (i.e., for resected DCIS) is not evaluable for breast imaging or biopsy.
 - a. _____ Participants must not have a recent diagnosis of invasive breast cancer, however, women with breast cancer who have been disease-free for more than 5 years are eligible. They will undergo standard follow-up evaluations appropriate to their recurrent cancer risk.
4. Participants must allow submission of core needle breast material (obtained per Section 7.3) for future use
5. Participants must have a baseline mammogram performed within 90 days prior to study entry, done on a digital mammography machine that shows either normal or benign findings. Participants with mammograms that are reported as suspicious for malignancy are eligible as long as the biopsy is negative.
6. Participants must have baseline mammographic density $> 10\%$ based upon the classification system (2 = 11-50%, "scattered fibroglandular densities"; 3 = 51-75%, "heterogeneously dense"; 4 = $>75\%$, "extremely dense"). Women with a baseline mammographic density of $\leq 10\%$ (1 = $\leq 10\%$, breasts are almost entirely fat) will not be eligible. Women with a BIRADS score of 4 will be considered eligible as long as the biopsy is benign.
7. Prior tamoxifen, raloxifene or aromatase inhibitor use is allowed provided treatment is completed at least 1 year prior to registration.
8. Participants must not have bilateral breast implants, but prior breast reduction surgery is allowed. (Breast implants are not allowed as they affect density measurements and because of the risk of rupturing the implant with biopsy).
9. Participants must have a ECOG Performance Status of 0 – 1 (see Section 11).
10. Prior anticoagulant therapy use is allowed provided therapy is discontinued at least 7 days prior to the breast biopsy in order to reduce the risk of bleeding. For subjects who have taken an anticoagulation within the past 7 days, INR (International Normalized Ratio) must be $\leq 1.5 \times$ institutional upper limit of normal and Prothrombin Time and Partial Thromboplastin Time \leq IULN prior to the breast biopsy.
11. No prior malignancy is allowed within the past five years except for the following: adequately treated skin cancer and *in situ* cervical cancer .

12. Participant must not be pregnant or nursing and must agree to use effective contraception. Hormone-based birth control (pills, patches or shots) are allowed, but switching birth control methods is discouraged while on-study as hormonal changes can affect mammographic density. Hormone replacement therapy is not allowed for post-menopausal female.
13. Individuals must not participate in any other clinical trial for the treatment or prevention of cancer unless they are no longer receiving the intervention and are in the follow-up phase only. Participants must also agree not to join such a trial while participating in this study.
14. All participants must be informed of the investigational nature of this study and must sign and give written informed consent in accordance with institutional and federal guidelines.

Exclusion Criteria

1. No prior malignancy within the past five years except for the following: adequately treated basal cell or squamous cell skin cancer and *in situ* cervical cancer. .
2. Prior Tamoxifen or Raloxifene or aromatase inhibitor or hormone replacement therapy use in the past 1 year

6 Treatment

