2.2 Risk Assessment

- Breast Risk Calculation using the modified Gail risk score [32, 33]. This model is an interactive tool designed to estimate a woman's risk of developing invasive breast cancer in her lifetime and the next 5 years.
 - <http://www.cancer.gov/bcrisktool/>
 - This model can only be used if there is no known diagnosis of DCIS or LCIS
- A patient with a diagnosis of lobular carcinoma in situ (LCIS) or atypical lobular or atypical ductal hyperplasia. Germline mutations of BRCA 1 or BRCA 2 genes. Germline mutations in the PTEN (cowden syndrome) and TP53(Li-Fraumeni syndrome)
- History of unilateral breast cancer 5 years ago
- At least 10% probability of carrying BRCA mutation

3 Objectives and endpoints

Primary

- To conduct a pilot breast cancer prevention study of hydroxytyrosol in women at increased risk of breast cancer.
- To assess whether mammographic density is reduced in pre or post menopausal women at high risk of breast cancer taking hydroxytyrosol for 1 year compared with baseline.

Secondary

- To assess the toxicity of hydroxytyrosol
- To evaluate FACT ES score baseline, 6 months and 1 year.
-

Exploratory objectives (Mandatory biopsy)

[figure not shown]
- To assess whether proliferation (Ki67 staining, Cdkn2a tumor suppressor, cyclin D1), is reduced in women at high risk of breast cancer after taking hydroxytyrosol for 1 year compared with baseline.
- To explore the difference in the expression of other biomarkers of apoptosis (Fas receptor, cleaved caspase-3, caspase-8, cytochrome c), enzymes related to oxidative stress (Fas receptor, cleaved caspase-3, caspase-8, cytochrome c), DNA damage by immunohistochemistry, Wnt signaling(LRP6, β -catenin, Sfrp proteins 1 to 5, DKK1, c-jun, c-myc) and stem cell pathway before and after drug therapy.
- To collect and bank breast tissue from women at high risk of breast cancer prior to and after treatment with hydroxytyrosol for future biomarker analysis.

Exploratory endpoint (MRI Breast Imaging)

- To assess breast MRI density pretreatment and 12 months post hydroxytyrosol therapy in subjects with available breast MRIs.

4 Study design

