4.1 Description of study design

A PILOT STUDY OF HYDROXYTYROSOL, A COMPONENT OF OLIVE OIL FOR BREAST CANCER PREVENTION IN WOMEN AT HIGH RISK OF BREAST CANCER

One hundred (100) pre and post-menopausal women at high risk of breast cancer who have declined tamoxifen, raloxifene or aromatase inhibitor (standard of care) will receive 25mg HT. Eligible women will have a 5 yr risk by Gail Model ≥ 1.7 , or 10% probability of BRCA mutation by BRCAPRO or similar model, or have a previous breast biopsy showing LCIS, atypical lobular or ductal hyperplasia, or have a known germline mutation in *BRCA1* or *BRCA2*. Patients with unilateral breast cancer 5 or more years prior to registration are also allowed. The main exclusion criteria include women who are pregnant or breast feeding, with diagnosis of any malignant disease, or with inability to take oral medication. The women will undergo a mammogram as well as a biopsy of normal breast tissue before and after taking study drug. This biopsy will be directed to the upper outer quadrant, which is typically a dense region. The primary endpoint of this study is change in mammographic density after treatment with HT. The Secondary endpoint will assess toxicity, apoptosis (Fas receptor, cleaved caspase-3, caspase-8, cytochrome c) and cell proliferation (Ki 67 staining, Cdkn2a tumor suppressor, cyclin D1), enzymes related to oxidative stress (ROS and related enzymes), DNA damage by immunohistochemistry, stem cell markers (CD44, CD24, and ALDH), and affection of Wnt signaling (LRP6, β -catenin, Sfrp proteins 1 to 5, DKK1, c-jun, c-myc) before and after drug therapy. If patients undergo a breast MRI before and/or after the completion of the drug, the images will be collected. The study drug will be supplied by PLThomas & Co.. The patients will have a study visit at 3, 6 and 12 months. The study visit will include a general history and physical exam, an assessment for safety and concomitant medications and pill

count. After completion of therapy, the patient will undergo a mammogram as well as a second breast biopsy.

5 Study Population

Each of the criteria in the following section must be met in order for a participant to be considered eligible for registration.

Study Duration:

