9. The random core needle biopsy is mandatory for study participation. All new patients on the study will undergo biopsy before and after the study drug. No attempt will be made to have the patients already on the study to undergo mandatory biopsy. All imaging is to be done prior to breast biopsy. If a patient is scheduled for a breast biopsy or surgery, tissue can be collected at that time.
10. A six month supply of the study drug will be dispensed at Day 1 visit and at 6 months. Compliance to be verified via pill count and pill diary.
11. The Fact ES questionnaire will be given at baseline, 6 months and at 12 months
12. Phone call to assess adverse events.
13. Physical exam to include abdominal circumference at baseline, 3, 6 and 12 months
14. Serum pregnancy test if premenopausal and has not had tubal ligation.

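### Inclusion item 2b ends by accepting any germline mutation, so entry as written does not ensure the high-risk population named in the primary objectives

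*Combined protocol and SAP*

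**What the plan says.** Section 5.1 item 2 sets the risk requirement: "Participants must have an elevated risk of breast cancer as defined by at least one of the following categories". It adds that the woman must have turned down tamoxifen, raloxifene or an aromatase inhibitor. One category is enough.

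Category 2b opens narrowly, with "A known deleterious mutation in *BRCA1*, *BRCA2*, *PTEN* or *TP53", and a note requires the participant herself to be a documented carrier.

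A final sentence then adds PALB2 and CHEK2 and continues "del 100C or any germline mutation".

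Two other sections describe the genetic route:

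- Section 2.2 lists "Germline mutations of BRCA 1 or BRCA 2 genes" and "Germline mutations in the PTEN (cowden syndrome) and TP53(Li-Fraumeni syndrome".
- Section 4.1 lists only BRCA1 and BRCA2: "or have a known germline mutation in *BRCA1* or *BRCA2".

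The primary objectives in section 3 concern women at increased, or high, risk of breast cancer. Footnote 9 to Table 7-1 says: "The random core needle biopsy is mandatory for study participation".

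**The concern.** The closing words of 2b carry no qualifier. They do not require the variant to be deleterious, or the gene to have anything to do with breast cancer. Item 2 defines elevated risk by its categories, so there is no separate risk check behind them. A rule that should select high-risk women therefore also accepts women whose only distinguishing feature is an inherited variant of no known relevance.

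Two things are at stake. The first is the match between the enrolled population and the one named in the primary objectives. The second is participant protection: new participants are to have a 14-gauge core biopsy of normal breast tissue before and after treatment and are not given the results. Their raised risk is the frame in which the study asks this of them.

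**Working it through.** **The plan's own figure.** The claim concerns eligibility wording, so the only related number is the stated power in section 9: 85% per menopausal group, with n = 50, null 25%, alternative 45% and a two-sided 5% level.

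- Arcsine approximation: Φ(2·[arcsin√0.45 − arcsin√0.25]·√50 − 1.96) = 84.9%.
- Normal approximation with continuity correction: Φ((0.20 − 1/100 − 1.96·√(0.25·0.75/50)) / √(0.45·0.55/50)) = 84.0%.
- Exact binomial, rejecting at 20 or more responders of 50: upper-tail error 0.0139, power 80.3%.

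The approximations reproduce the stated 85%. None of the inputs refers to risk status or mutation type, so the figure neither supports nor undermines the point.

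**The four texts on the genetic route, side by side.**

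| Place | Genes | Must be deleterious? |
|---|---|---|
| 2.2 | BRCA1, BRCA2, PTEN, TP53 | not stated |
| 4.1 | BRCA1, BRCA2 | not stated |
| 5.1 item 2b, opening | BRCA1, BRCA2, PTEN, TP53 | yes, with documented carrier status |
| 5.1 item 2b, last sentence | PALB2, CHEK2, then any | no |

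**Does anything restore a limit?**

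1. The opening of 2b does not. Every woman who meets it also meets the last clause, so its limits no longer decide anything.
2. The note in 2b mentions breast cancer susceptibility genes, but it deals with testing when a relative carries a mutation. It stands before the open clause and does not govern it.
3. The elevated-risk lead-in of item 2 does not, because the categories define that risk.
4. The requirement to have declined preventive therapy narrows the group in practice but sets no risk threshold.
5. No other inclusion or exclusion item in 5.1 requires the mutation to raise breast cancer risk.

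**Size.** If k women in a group of 50 entered on the clause alone, with response rate q, and the others responded at rate p, the expected group proportion would be [(50 − k)·p + k·q]/50. One woman is 1/50 = 2% of the group, so her result moves the observed proportion by at most two percentage points. The documents give neither k nor q, and nothing in them says that q differs from p. The effect on the result or on power cannot be calculated.

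**Prior breast cancer.** Section 2.2 lists unilateral breast cancer 5 years ago as a risk category. Section 4.1 says: "Patients with unilateral breast cancer 5 or more years prior to registration are also allowed". Section 5.1 item 3a, placed under the requirement for an evaluable breast, accepts women disease-free for more than 5 years. The intervals differ (5 years, 5 or more, more than 5). Item 2 does not list this history, and section 5 requires every criterion to be met, so it is unclear whether 3a alone satisfies item 2.

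**The case against.** The strongest reply is that the intent is plain. The clause follows PALB2 and CHEK2, sits under a heading about breast cancer risk, and comes after a note about breast cancer genes. The principal investigator or a designee reviews eligibility before enrolment, and few average-risk women would be in a position to decline a preventive drug. All of this stands, and it makes a large practical effect unlikely. It does not make the text precise: eligibility is judged against the written criteria, and the clause says any.

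It can also be said that section 4.1 is a summary, that section 5 holds the governing criteria, and that 2.2 does not ask for a deleterious mutation either. That is fair. It means the differences between sections are partly a matter of detail, but the governing text is the one with the fault.

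The biopsy burden should not be overstated. Footnote 9 exempts women already on study when the requirement began, and tissue from an already scheduled biopsy or operation may be used instead.

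A reader might infer that a woman whose only risk factor is an old breast cancer is shut out by 5.1. The documents do not support that, because item 3a calls such women eligible. What remains is the unclear relation between 3a and item 2, and the differing intervals.

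**Conclusion.** The point holds as a fault in the eligibility wording. As written, a woman with an unrelated or non-deleterious variant who has declined preventive endocrine therapy meets item 2. Entry therefore does not ensure the population named in the primary objectives. This rests on a literal reading of item 2b and on the absence of any other limiting criterion in 5.1.

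A reader might go further and infer that average-risk women were enrolled in number, that the tissue-marker findings are diluted, or that the power statement is wrong. None of these is supported. The documents do not show that anyone entered through the clause, and nothing in them ties density response or marker change to mutation type. The primary endpoint is change within each woman, and item 6 requires baseline density above 10% whatever the route of entry. The practical effect may well be small. The reason to act is that the repair is cheap and the present rule depends on the reader's goodwill.

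**What to change.** In item 2b, replace the open clause with *or a documented deleterious mutation in another hereditary breast cancer susceptibility gene*, and apply the documented-carrier note to every gene listed. Align the gene lists in sections 2.2, 4.1 and 5.1.

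If any woman has already entered on the clause alone, keep her in the main analysis, since she met the criteria in force. Report the density result without her as a sensitivity analysis beside the full result.

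Separately, and as a minor matter, reconcile 2.2, 4.1 and 5.1 item 3a on prior breast cancer, and state whether 3a by itself satisfies item 2. Editing 2.2 and 4.1 alone would leave 3a standing.

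The cost is a one-line eligibility amendment plus consistency edits. The downside is that a few otherwise eligible women may be lost.

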2.1 Methodology

The mammographic density will be classified by two different methods. Firstly, according to the American College of Radiology's Breast Imaging—Reporting and Data System (BIRADS), and secondly, by using the Cumulus software package developed by the Ontario Cancer Institute to assess percent density as a continuous measure (0-100% scale). The mammograms will be read for research purposes only. They will be read for clinical purposes at the time of the mammogram. The mammograms will be independently reviewed by two radiologists specializing in breast imaging. Quantitative classification of mammographic parenchyma will be based on radiological assessment after digitizing mammograms and measuring percentage density[28, 31].

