reported as a follow-up to that event regardless of when it occurs. The follow-up information should describe whether the event has resolved or continues, if and how it was treated, whether the blind was broken or not (if applicable), and whether the patient continued or withdrew from study participation.

If the SAE is not previously documented in the Hydroxytyrosol Investigator Brochure or Package Insert (new occurrence) and is thought to be related to the study drug, may urgently require further information from the investigator for Health Authority reporting. TMHCC and TMHRI may need to issue an Investigator Notification (IN), to inform all investigators involved in any study with the same drug that this SAE has been reported. Suspected Unexpected Serious Adverse Reactions (SUSARs) will be collected and reported to the competent authorities and relevant ethics committees in accordance with Directive 2001/20/EC or as per national regulatory requirements in participating countries.

For Comparator Drugs/Secondary Suspects (Concomitant Medications), all serious adverse experiences will be forwarded to the comparator drug company by the investigator.

9 Statistical methods

Study Design and Sample Size. This is a single-arm, pilot breast cancer prevention study of hydroxytyrosol in women at increased risk of breast cancer. Our primary study endpoint will be defined as proportion of women who exhibit a 10% absolute reduction in mammographic density at one-year of follow-up (Cuzick JNCI 2011). For each of the post and pre-menopausal group of women, we will assume under the null hypothesis that 25% of women will exhibit a response (at least a 25% reduction from baseline) versus an alternative hypothesis equal to 45% based on data presented from Cuzick (JNCI 2011). Under these assumptions, a sample of 50 pre-menopausal and 50 post-menopausal women will provide 85% power based on a two-sided test for a single proportion with 5% significance level for each group of women.

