Statistical Analysis. Demographics and pre-treatment characteristics will be summarized for 50 premenopausal & 50 postmenopausal women using descriptive statistics. Mammographic density levels at baseline and follow-up time-points as well as categorized levels based on BIRAD criteria will also be summarized using means, standard deviations and proportions. Change from baseline levels of breast density will be analyzed using paired tests while the proportion of women who exhibit at least a 10% absolute reduction from baseline will be calculated along with 95% binomial confidence intervals for each group of women.

Correlative endpoints including Ki-67, apoptosis, Wnt signaling and stem cell pathway markers will likewise be summarized descriptively at each time point of follow-up. Correlations between these markers and with mammographic density levels will be assessed using Spearman or Pearson's correlation coefficients. Change from baseline levels will be analyzed using paired t-test or Wilcoxon-signed rank test.

Multivariate analysis to adjust for demographic/clinical characteristics, specifically age or menopausal status (pre, peri, and post) will likewise be considered using logistic regression for analyzing proportion of women with response or using linear regression models for analysis of quantitative levels of mammographic density. Given the pilot nature of this study, these multivariate analyses will be considered exploratory.

Expected outcome: We expect a decrease in apoptosis, cell proliferation, in post-treatment breast tissue in comparison to pre-treatment. Our previous data reveal an inhibition of Wnt signaling by HT, thus we expect a change in this signaling in this prevention study.

Potential pitfalls, and resolutions: If we do not have enough breast tissue for all determinations, it will be difficult to measure mRNA levels. In such a scenario, we can determine the expression of Sfrp proteins only by multiplex nucleic acid *in situ* hybridization technology (RNAscope) in paraffin embedded tissue slides.

CONFIDENTIAL

10 References:

1. Siegel, R., D. Naishadham, and A. Jemal, Cancer statistics, 2012. *CA Cancer J Clin.* 62(1): p. 10-29.
2. Anderson, D.E., Genetic study of breast cancer: identification of a high risk group. *Cancer*, 1974. 34(4): p. 1090-7.
3. Jatoi, I. and A.B. Miller, Why is breast-cancer mortality declining? *Lancet Oncol.* 2003. 4(4): p. 251-4.

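### Entry starts just above 10% density but response is a 10-point absolute fall, so the responder proportion depends on baseline density, which the plan neither models nor ties to its 25% and 45% rates

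*Combined protocol and SAP*

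**What the plan says.** **Entry.** Item 6 of Section 5.1 requires baseline density above 10%, "based upon the classification system (2 = 11-50"% being the lowest category let in. Only the lowest category is shut out: women at 10% or less, whose "breasts are almost entirely fat) will not be eligible".

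**Response.** The sample-size paragraph of Section 9 defines the primary endpoint as the "proportion of women who exhibit a 10% absolute reduction in mammographic density at one-year of follow-up". The analysis paragraph uses the same scale: "the proportion of women who exhibit at least a 10% absolute reduction from baseline will be calculated", with a 95% binomial interval for each menopausal group.

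**Rates.** The hypothesis sentence describes response differently. Under the null, "25% of women will exhibit a response (at least a 25% reduction from baseline"), "versus an alternative hypothesis equal to 45"%. On this basis "a sample of 50 pre-menopausal and 50 post-menopausal women will provide 85% power", using a two-sided 5% test of one proportion in each group.

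**Measurement.** Section 2.1 lists two methods, BI-RADS categories and Cumulus software "to assess percent density as a continuous measure (0-100% scale"). No section says which one decides response.

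**Adjustment.** The exploratory logistic and linear models in Section 9 single out age or menopausal status. Baseline density is not named. Paired tests of change in density are also planned.

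**The concern.** The entry threshold and the required fall are almost the same number. A woman who enters near the threshold counts as a responder only if nearly all her measured density disappears. A woman at 50% needs to lose one fifth of hers. The same drug effect, in relative terms, can therefore be scored as failure in one woman and success in the other.

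This is a single-arm trial judged against a fixed 25%. No control group shares the baseline mix, so the observed proportion can be interpreted only if the 25% and 45% rates were derived for the same response definition and a similar spread of baseline density. The plan shows neither. The result in each group could then depend partly on how many low-density women happened to enrol.

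**Working it through.** **1. The plan's own power figure.** Inputs from Section 9: n = 50 per group, null 0.25, alternative 0.45, two-sided 5%. By the arcsine approximation,

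power = Φ(2(arcsin√0.45 − arcsin√0.25)√50 − 1.96) = Φ(2 × 0.2117 × 7.071 − 1.96) = Φ(1.03) = 84.9%.

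The stated 85% is reproduced.

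**2. Fall required, by baseline b.** Under the absolute definition the relative loss needed is 10/b. Under the other definition, read as relative, the points needed are 0.25b.

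| Baseline | Relative loss for a 10-point fall | Points for a 25% relative fall |
|---|---|---|
| 11% | 91% | 2.75 |
| 15% | 67% | 3.75 |
| 20% | 50% | 5.0 |
| 30% | 33% | 7.5 |
| 40% | 25% | 10.0 |
| 50% | 20% | 12.5 |
| 75% | 13% | 18.75 |

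The definitions agree where 0.25b = 10, that is at b = 40%. Below 40% the 10-point rule is stricter, and above 40% the relative rule is stricter. A rate that holds for one need not hold for the other.

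**3. The protocol's own effect size.** Section 2 cites a 30% reduction in density for the highest olive oil tertile, without stating the scale. If it is relative, 0.30b reaches 10 points only when b is at least 33.3%. A woman at 20% with that full effect would fall 6 points and be scored a non-responder.

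**4. What a non-responding share would cost.** Let a share f of a group have too little density to respond, and let the rest respond at 45%. The group rate is 0.45(1 − f). The documents do not give f, so it is an assumption shown as a range. Section 9 does not say which binomial interval or test will be used, so two decision rules are shown:

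- At least 20 of 50: the exact (Clopper-Pearson) lower limit is 26.4% at 20/50 and 24.7% at 19/50. Upper-tail error at 25% is 1.4%.
- At least 19 of 50: the normal test with null variance gives z = (0.38 − 0.25)/√(0.25 × 0.75/50) = 2.12 at 19/50 and 1.80 at 18/50. Exact upper-tail error is 2.9%.

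| f | Group rate | P(at least 20 of 50) | P(at least 19 of 50) |
|---|---|---|---|
| 0 | 45% | 80% | 87% |
| 5% | 42.75% | 70% | 79% |
| 10% | 40.5% | 58% | 69% |
| 20% | 36% | 33% | 44% |
| 30% | 31.5% | 13% | 20% |

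The gap between 80% and 87% at f = 0 comes from the choice of rule, not from low-density women. The effect at issue is the fall down each column.

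**5. The condition on step 4.** The model gives 45% only to women with room to respond. If 45% already describes a population with a similar share of low-density women, the group rate is 45% as planned and nothing is lost.

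**The case against.** A reader might infer that low-density women cannot respond and so dilute the primary proportion. The documents do not support that. Item 6 requires density above 10%, so a 10-point fall is arithmetically possible for every woman whose measured density meets it. The lowest admitted category runs to 50%, where the required loss is only 20%. Section 9 applies 25% and 45% to each whole menopausal group, so low-density women may already be allowed for. Also, the sentence carrying those rates uses the 25% reduction; if that is relative and governs, the problem near the entry threshold disappears.

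A reader might also suppose that a woman placed in the second category by BI-RADS could have a Cumulus value below 10% and be unable to respond at all. Item 6 states both a category and a percent threshold and does not say which reading governs, so this is possible but not shown. Nor is a comparison between menopausal groups a primary test: each group is tested separately, and menopausal status enters only exploratory models.

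Finally, the planned paired tests already use change in density in all women, without scoring anyone as a failure.

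All of this stands, and it limits the claim. It does not remove the dependence of the 10-point endpoint on baseline density. The absolute definition is the one labelled primary and the one in the analysis paragraph. The competing definition means the rates and the endpoint may not belong together.

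**Conclusion.** The point holds as a gap in definition and justification. Under the stated primary endpoint, the relative loss needed ranges from 91% at a baseline of 11% to 13% at 75%. The plan names no baseline-density adjustment, and it attaches its 25% and 45% rates to a response worded differently.

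A loss of power is conditional. It requires that the 45% rate apply only to women with room to respond. On that assumption, a non-responding share of 10% to 20% takes the chance of excluding 25% from 80% to between 58% and 33%, or from 87% to between 69% and 44%, depending on the decision rule. If the rates come from a comparable baseline mix and the same definition, the stated 85% stands. The documents give neither that mix nor the expected one in this trial, so neither the presence nor the size of a loss can be established from them.

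The facts do not require a higher entry cut-off, or a primary test restricted to denser women. No cut-off such as 20% has a source in the documents, and a woman at 20% would still have to lose half her density. Restriction would also cost precision: with 40 women and a true rate of 45%, an exact rule (at least 17 of 40) has 68% power.

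**What to change.** In Section 9:

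1. Use one response definition throughout, measured by Cumulus. Confirm that the 25% and 45% rates belong to that definition and to a population with a comparable spread of baseline density.
2. Add baseline Cumulus density as a covariate in the planned logistic and linear models.
3. Pre-specify, as a descriptive result, the responder proportion by baseline Cumulus density within each menopausal group. Present the already planned paired mean change in Cumulus density, in all women, beside it.

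Keep the primary test in all 50 women per group and leave eligibility unchanged.

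The cost is small: wording in Section 9 and a little more analysis of readings the protocol already plans to take. The estimates by baseline density will be imprecise, because each rests on only part of a group of 50, and should be labelled descriptive. If the rates turn out to belong to the other definition or to a different baseline mix, the power statement must be recalculated.
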